5.4 Management of test drugs

5.4.1 Distribution and storage of test drugs

The distribution and management of test drugs shall be carried out according to the steps described in the Protocol. According to the requirements of registration regulations, only the subjects enrolled in the trial can get the test drugs; and only authorized personnel (drug administrators) in each research center can provide and keep the test drugs. All test drugs shall be stored in a safe place, and only a few personnel related to the test are allowed to get in and out for the drugs. The authorized test personnel shall ensure that the amount of the test drugs is consistent with that on the test drug requisition.

All the test drugs shall be locked and stored in a safe, dark and dry place before distribution. The storage temperature shall be below 25°C and 30°C respectively for tacrolimus and mycophenolate mofetil. Each research center shall have a registration form for drug reception and drug distribution, which shall always be kept by a person (drug administrator) designated by the research center. The drug administrator shall ensure that the drugs are intact when they are distributed to the subjects, and the remaining period of validity shall be at least 3 months.

5.4.2 Count of test drugs

The drug administrator has the responsibility to ensure that the quantity of drugs is consistent with the registered quantity, and has the responsibility to keep the drug registration records. According to the requirements of registration laws and regulations, the drug administrator shall keep the drug inventory and verification records throughout the research process, including the records of the quantity of test drugs received from Hangzhou Zhongmeihudong Pharmaceutical Co., Ltd., the quantity of test drugs stored and/or distributed, and the quantity of drugs returned by the subjects to the research center.

When the test drugs arrive at each research center, the drug administrator shall sign on the drug reception form to confirm the receipt of test drugs for trial use. The form includes but is not limited to: drug name, batch number, quantity, receiving date and drug inspection report.

The drug administrator shall record all the distributions on the distribution checklist. At the end of this research, the quantity of the test drugs on the checklist shall be consistent with the quantity sent by the Sponsor, the quantity of drugs kept in the center, the quantity sent to the subjects and the quantity returned. At the same time, a reasonable explanation shall be given for any discrepancy. During this research, the drugs shall be recycled in stages, and after this research, all empty boxes for used drugs and unopened drugs shall be returned to the Sponsor, with signatures on the return drug form. The recovered drugs shall be destroyed together in the factory of the

Sponsor. The destruction of drugs is carried out by authorized special personnel who shall have a certain sense of prevention against the possible dangers in drug destruction. At the same time, they shall not begin such operation without written authorization from the Sponsor. The whole process of destroying drugs will be completely recorded and archived.

5.4.3 Packages and labels of test drugs

The test drugs are packaged by Hangzhou Zhongmeihuadong Pharmaceutical Co., Ltd. according to the relevant laws and regulations, and the labels of the test drugs comply with the requirements of relevant laws and regulations.

5.5 Medication adherence

Distribute the tacrolimus capsules or mycophenolate mofetil dispersible tablets according to the Dosage and Administration specified in the Protocol. The quantity of drugs distributed before administration, the quantity of drugs used and the quantity returned by each subject shall be recorded in detail. Including the following content:

A: Name, date and quantity of drugs distributed to subjects

B: Name, date and quantity of drugs returned by subjects

The clinical research associate shall check the inventory drugs, returned drugs and drug distribution records of the research center on a regular basis. At the end of this research, the remaining drugs, returned drugs and their packages shall be counted and recovered.

The medication adherence is calculated as follows, and shall be ranging from 80% to 120%:

$$\text{adherence} = \frac{\text{actual administration}}{\text{planned administration}} \times 100\%$$

At each follow-up, the investigators shall emphasize the importance of medication adherence to the subjects.

6. Test process and steps

The selected patients are randomly divided into two groups. Patients in FK506 Group receive tacrolimus capsules and steroids for one year; and patients in MMF Group receive mycophenolate mofetil dispersible tablets and steroids for one year. Both groups follow the "clinical trial flow chart" in operation.

7. Evaluation of efficacy and safety

7.1 Primary efficacy outcomes

1-year relapse-free survival

7.2 Efficacy evaluation

7.2.1 Primary observation outcomes: 1-year relapse-free survival

7.2.2 Secondary observation outcomes:

- (1) Frequency of relapses; the time of the first relapse after enrollment; relapse-free **survival** in the first six months after enrollment;
- (2) Renal function: Serum creatinine and glomerular filtration rate (eGFR, see Appendix 1 for the calculation method)
- (3) Cumulative steroid dosage: The total amount of steroids taken during this research and the total amount of steroids in the first half of the year
- (4) Others: Blood pressure (see Appendix 2 for details), height, weight, blood lipid, hemoglobin, blood albumin, urinary protein/creatinine (morning urine), etc.
- (5) Adverse reaction
- (6) 24hr urinary protein quantification (applicable to subjects > 3 years old)

7.2.3 Efficacy criteria

- Complete remission (CR): Completely normal in blood biochemistry test and urine examination;
- Partial remission (PR): Urinary protein positive < (+++);
- No remission (NR): Urinary protein positive \geq (+++).

7.2.4 Relapse criteria

For 3 consecutive days, morning urinary protein changes from negative to (+++) or (++++) , or 24hr urinary protein quantification \geq 50 mg/kg, or urinary protein/creatinine (mg/mg) \geq 2.0.

7.3 Safety evaluation

Changes of vital signs: Respiration and heart rate.

Various indexes in laboratory examination: Blood and urine routine examination, liver function, renal function, ECG, chest X-ray examination.

Clinically reported adverse events and adverse reactions.

8. Reporting adverse events

8.1 Definition of adverse events

Adverse event (AE) refers to the adverse medical conditions or deterioration of the original medical condition after or during drug treatment, regardless of whether there is a causal relationship with the drug. Adverse medical conditions can be symptoms (such as nausea, and chest pain), signs (such as tachycardia, and hepatomegaly), or abnormal examination results (such

as laboratory examination, and ECG). In clinical researches, AE can occur at any time, including the adverse medical conditions in the screening period, even if no study treatment is received.

The term AE includes severe ones and non-severe ones.

8.1.1 Concerned adverse reactions of test drug FK506:

Adverse reactions associated with immunosuppressive drugs are often difficult to be determined due to the underlying diseases of patients and combined use of multiple drugs at the same time. The following adverse reactions are reversible, or can be reduced or eliminated after dose reduction. Compared with intravenous administration, oral administration has a lower incidence of adverse reactions.

Cardiac abnormalities

Common: Ischemic coronary artery disease, and tachycardia; Unusual: Ventricular arrhythmia and cardiac arrest, heart failure, cardiomyopathy, ventricular hypertrophy, supraventricular arrhythmia, palpitation, abnormal ECG, abnormal heart rate and pulse; Rare: Pericardial effusion; Very rare: Abnormal echocardiography.

Blood and lymphatic system abnormalities

Common: Anemia, leucopenia, thrombocytopenia, leucocytosis and abnormal erythrocyte analysis; Unusual: Abnormal coagulation function, pancytopenia, and neutropenia; Rare: Thrombotic thrombocytopenic purpura, and low prothrombin; Unknown: Pure red cell aplasia, agranulocytosis, and hemolytic anemia.

Neurologic abnormalities

Very common: Tremor, and headache; Common: Epilepsy, disturbance of consciousness, paresthesia and dullness, peripheral neuropathy, vertigo, dysgraphia and nervous system disorders; Unusual: Coma, central nervous system hemorrhage and cerebrovascular accident, paralysis and local anesthesia, encephalopathy, abnormal language function and cognitive impairment; Rare: Hypertonia; Very rare: Myasthenia.

Eye and ear abnormalities

Common: Blurred vision, photophobia, and eye discomfort; Unusual: Cataract; Rare: blindness, abnormal ear and labyrinth; Common: Tinnitus; Unusual: Hearing retardation; Rare: Neurogenic deafness; Very rare: Hearing loss.

Respiratory, chest and mediastinum abnormalities

Common: Dyspnea, abnormal lung parenchyma, pleural effusion, pharyngitis, cough, nasal congestion and inflammation; Unusual: Respiratory failure, respiratory diseases, and asthma; Rare: Acute respiratory distress syndrome; Unknown: Interstitial lung disease, and pulmonary embolism.

Gastrointestinal abnormalities

Very common: Diarrhea, and nausea; Common: Gastrointestinal inflammation, gastrointestinal ulcer and perforation, gastrointestinal bleeding, stomatitis and ulcer, ascites, vomiting, abdominal pain, dyspepsia, constipation, abdominal distention, loose stools and other gastrointestinal symptoms and signs; Unusual: Paralytic intestinal obstruction, peritonitis, acute and chronic pancreatitis, elevated blood amylase, gastroesophageal reflux and abnormal gastric emptying; Rare: Intestinal obstruction, and pancreatic pseudocyst.

Renal and urinary abnormalities

Very common: Kidney injury; Common: Renal failure, oliguria, tubular necrosis, toxic nephropathy, and bladder and urethral symptoms; Unusual: Anuria, and hemolytic uremic syndrome; Very rare: Kidney disease, and hemorrhagic cystitis; Unknown: Membranous glomerulonephritis, hydronephrosis, nephromegaly, and nephrotic syndrome.

Skin and subcutaneous tissue abnormalities

Very common: Pruritus, rash, hair loss, acne, and hyperhidrosis; Unusual: Dermatitis, and photosensitivity; Rare: Toxic epidermal necrolysis (Lyell's syndrome); Very rare: Stevens-Johnson syndrome; Unknown: Melanoderma.

Skeletal muscle and connective tissue abnormalities

Common: Joint pain, muscle spasm, limb pain, and back pain; Unusual: Joint disorder; Unknown: Bone defect, kyphosis, patellar pain syndrome, and rhabdomyolysis.

Endocrine abnormalities

Rare: Hirsutism; Unknown: Diabetes ketoacidosis.

Metabolic and nutritional abnormalities, and other electrolyte abnormalities

Very common: Hyperglycemia, diabetes, and hyperkalemia; Common: Hypomagnesemia, hypophosphatemia, hypokalemia, hypocalcemia, hyponatremia, fluid retention, hyperuricemia, decreased appetite, anorexia, metabolic acidosis, hyperlipidemia, hypercholesterolemia, and hypertriglyceridemia. Other electrolyte abnormalities: Unusual: Dehydration, hypoproteinemia, hyperphosphatemia and hypoglycemia.

Infection and invasion

Like other potent immunosuppressants, tacrolimus administration shows an increased risk of infection (viruses, bacteria, fungi and protozoa). Existing infections may be aggravated, and the systemic and local infections may occur. Patients treated with immunosuppressants, including tacrolimus, have been reported to have BK virus-related nephropathy and JC virus-related progressive multifocal leukoencephalopathy (PML).

Injury, intoxication and operation complications

Benign, malignant and unclear tumors (including cysts and polyps). Patients treated with immunosuppressants have an increased risk of malignant tumors. Benign and malignant tumors,

including EBV-related lymphoid hyperplasia and skin malignancies, have been reported to have possible association with the tacrolimus treatment.

Vascular abnormalities

Very common: Hypertension; Common: Bleeding, thrombus and local ischemia, peripheral vascular abnormalities, and hypotension; Unusual: infarction, limb deep vein thrombosis, and shock.

General abnormalities and administration site symptoms

Common: Weakness, fever, edema, pain and discomfort, elevated blood alkaline phosphatase, weight gain, and body temperature sensation disorder; Unusual: Multiple-organ failure, influenza like symptoms, temperature intolerance, chest compression, tension, paresthesia, elevated blood lactate dehydrogenase and weight loss; Rare: Thirst, fall, reduced activity, and ulcer; Very rare: Increased adipose tissue; Unknown: Death or sudden cardiac death, and abnormal gait.

Immune system abnormalities and hepatobiliary abnormalities

Allergic and anaphylactic reactions are observed in patients treated with tacrolimus.

Common: Abnormal liver function, cholestasis and jaundice, hepatocyte injury, hepatitis and cholangitis; Rare: Hepatic artery thrombosis, and venous occlusive liver disease; Very rare: Liver failure, and biliary stricture;

Reproductive system and breast abnormalities

Unusual: Dysmenorrhea and uterine bleeding; Unknown: Benign prostatic hyperplasia, and mental disorders; Very common: Insomnia; Common: Anxiety, confusion and disorientation, despondency, depression, emotional instability and disorder, nightmares, hallucinations and mental disorders; Unusual: Mental abnormality; Unknown: Aggressive behavior, and agitation.

8.1.2 Concerned adverse reactions of test drug MMF:

Infection

It refers to the local tissue inflammatory reaction and systemic inflammatory reaction caused by bacteria, viruses, fungi, parasites and other pathogens invading the human body. Serious life-threatening infections, such as meningitis and infective endocarditis, are occasionally reported, and some evidences show that certain types of infections, such as conjugated and atypical waste bacilli infections, lay have a high incidence

Gastrointestinal adverse reactions

Gastrointestinal adverse reactions include nausea, vomiting, dyspepsia, abdominal pain, constipation, upper and lower gastrointestinal discomfort, gastrointestinal inflammation, gastroduodenal ulcer, gastrointestinal bleeding and perforation, etc. Colitis (sometimes caused by cytomegalovirus), pancreatitis, and individual cases of intestinal villus atrophy.

Blood system and immune system

In patients treated with this product in combination with other immunosuppressants, pure red cell aplasia (PRCA) and hypogammaglobulinemia have been reported.

Congenital diseases

Congenital malformations, including ear, face, heart and nervous system abnormalities, have been reported in the children of mothers treated with this product and other immunosuppressants during pregnancy. There are also reports of spontaneous abortion in early pregnancy.

Pregnancy, puerperium and perinatal periods

Spontaneous abortion has been reported in patients (mainly in early pregnancy) exposed to mycophenolate mofetil.

Malignant tumors

Patients taking this product as part of immunosuppression for immunosuppressive regimen, including the patients with combined use of drugs, have an increased risk of lymphoma and malignant tumors, especially skin tumors. In a controlled clinical trial for patients with a follow-up of at least 1 year after kidney, heart and liver transplantation, lymphoproliferative disease or lymphoma develop in 0.4% to 1% of the patients treated with this product (2g or 3g daily) in combination with other immunosuppressants. Non-melanoma skin cancer develops in 1.6% to 3.2% of the patients; 0.7% to 2.1% of patients have other types of malignant tumors. In the 3-year safety data of kidney and heart transplantation patients, the incidence rate of malignant tumors shows no unexpected difference with that in the 1-year data. All the patients with liver transplantation are followed up for more than 1 year and less than 3 years. In the controlled trial of refractory renal transplantation, the incidence of lymphoma is 3.9% with an average follow-up of 42 months.

Children (aged 3 months to 18 years)

In a clinical study of 100 pediatric patients aged 3 months to 18 years, the type and frequency of adverse reactions after oral administration of 600 mg/m² mycophenolate mofetil (BID) are generally similar to those observed in adult patients with daily administration of 1g mycophenolate mofetil (BID). However, as compared with the adult patients, the following treatment-related adverse events with a frequency of 10% are more common in the pediatric population, especially in children under the age of 6 years, including diarrhea, leukopenia, sepsis, infection and anemia.

Elderly patients (≥ 65 years old)

As compared with young people, the elderly, especially the elderly patients receiving this product as part of the combined immunosuppressive regimen, have an increased risk of some infections (including cytomegalovirus tissue invasion disease), possible gastrointestinal bleeding and pulmonary edema.

Toxicity criteria

Based on the revised standard of the World Health Organization (WHO) on the grading of acute and subacute toxicity of drugs.

8.2 Definition of serious adverse event

Serious adverse event (SAE) refers to the AE occurring at any stage of this research (i.e. screening period, follow-up period) and complying with one or more of the following criteria:

- Causing death
- Immediate life-threatening
- Requiring hospitalization or extension of the original length of stay
- Causing sustained or significant deformity/disability, or seriously impairing the ability to complete normal life functions
- Congenital malformation or defect at birth
- An important medical event that may cause harm to the patient or may require medical intervention to prevent one of the above outcomes

8.3 Records of adverse events

The information of AEs to be collected in this research includes the following aspects:

- Endpoint event
- Adverse events related to the test drugs (according to the judgment of the investigators)
- Serious adverse event

Cycle of adverse event collection

The collection of AEs and adverse drug reactions (DAEs) of concern will be carried out throughout this research, from randomization to site close-out visit (SCV, included).

SAE records will be carried out throughout this research, from the time of signing the Informed Consent Form to SCV (included).

Follow-up of unresolved adverse events

If any AE, DAE and SAE of concern remain unresolved at the patient's last study visit, the investigators shall follow up these events in accordance with the medical instructions as required for medical needs in this research, but it is not necessary to record further in the electronic case report form (eCRF). If deemed necessary, the Sponsor reserves the right to obtain the additional information on unresolved AE/SAE of concern.

Variables

For each non-serious AE and DAE of concern, the following variables will be collected:

- AE (verbatim record);
- AE start and end dates;
- Maximum intensity;

- Whether the AE is serious;
- The investigators' assessment of the causal relationship with the test drug (yes or no);
- Measures and outcomes taken for the test drug

In addition, the following variables will be collected for SAE:

- Date when AE meets SAE criteria;
- Date when the investigators find SAE;
- Reasons for classifying AE as SAE;
- Date of admission;
- Date of discharge;
- Possible causes of death
- Date of death;
- Autopsy performed (if any);
- Autopsy results
- AE description
- Assessment of causality with this research procedure;
- Assessment of causality with the other drugs

It is important to distinguish serious AE from severe AE. Severity is the index of intensity evaluation, while seriousness is defined according to the criteria in Section 8.2. AE with severe intensity is not necessarily serious. For example, nausea for several hours may be considered as severe nausea, but not SAE. On the other hand, a stroke that results in only a limited degree of disability may be considered as a mild stroke, but should be considered as SAE.

The definition of intensity classification is as follows:

1. Mild (signs or symptoms are felt but easily tolerated)
2. Moderate (the degree of discomfort is enough to interfere with normal activities)
3. Severe (resulting in disability and inability to perform normal activities)

Collection of causalities

The investigators will assess the causalities between the test drugs and each case of AE, and answer the following questions with "Absolutely related, Probably related, Possibly related, Possibly unrelated, and Unrelated".

"Do you think there is a reasonable possibility that the event is caused by the test drug?"

For SAE, the causalities between the event and other drugs and research procedures also need to be evaluated. Note: for SAE related to any research procedure, causality should be "possibly related".

Adverse events based on signs and symptoms

All concerned AEs (see sections 8.1.1 and 8.1.2), including those spontaneously reported by the patients, those reported in response to the open-ended question by the investigators, "Have you

had any health problems since the last visit/inquiry?", or those found through observation will be all collected and recorded in eCRF. In the collection of AE information, the list of signs and symptoms shall be preferred as the record of diagnosis (if possible). However, if the diagnosis is known and there are other signs or symptoms not usually present in the diagnosis, the diagnosis and each other sign or symptom shall be recorded separately.

Adverse events based on examination and inspection

During this research, the laboratory safety assessment will not be carried out routinely (except at baseline), but can be carried out at the discretion of the investigators. When an AE, DAE, SAE or potential endpoint of concern is involved, different assessments may be required, including local laboratory assessment, and appropriate collection is needed before entry into eCRF.

The examination results of vital signs mandated by the Protocol shall be summarized in the clinical study report (CSR). Therefore, when the laboratory test values and protocol-mandated vital signs evaluation by the investigators show that the results are worse than the baseline level and meet the AE criteria or when they act as are the reasons for discontinuing the test drug treatment, such situations will be reported as AE.

If the deterioration of laboratory test values/vital signs is related to clinical signs and symptoms, the signs and symptoms will be reported as AE and relevant laboratory results/vital signs will be used as supplementary information. Investigators shall use clinical terms rather than laboratory terms (e.g. renal failure rather than elevated creatinine) as much as possible in the report. If no clinical signs or symptoms are present, the clinically relevant deterioration of non-mandatory parameters shall be reported as AE and SAE.

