8.1.3. Primary efficacy analysis

Logrank test is used for the analysis of relapse-free survival rate which is then used as a covariate for stratification by Sites. HR and its 95% confidence interval (CI) are calculated with Cox proportional hazard model to estimate the efficacy, the confidence interval is applied to verify the superiority of the experimental group and the control group, with a cut-off value of 1 (risk ratio). The model incorporates the same covariate as the Logrank test for fitting, and the definition method of covariates is also the same as that in the Logrank test. The Kaplan-Meier curve of relapse-free survival is drawn by treatment groups. The 1-year relapse-free survival rate and its confidence interval are then calculated.

Calculation rules for the main efficacy indicators:

- If relapse occurred within 9 visits (within 364 ± 7 days) or unscheduled visits within 365 days of randomization, defined as the occurrence of endpoint events. Time of relapse = date of relapse - Random date + 1, calculated by days.
- If the visit stipulated in the protocol was not completed within 9 visits (within 364 ± 7 days) due to loss of follow-up midway or withdrawal or other reasons, it is defined as censoring. Time of

censoring = date of withdrawal - random date + 1, calculated by days.

- If the visit stipulated in the protocol was not completed within 9 visits (within 364 ± 7 days) due to death in the trial, it is defined as censoring. Time of censoring = Death date - random date + 1, calculated by days.
- If the visit stipulated in the protocol was completed and there is no relapse within 9 visits (within 364 ± 7 days), it is defined as censoring. Time of censoring = date of visit 9 (within 364 ± 7 days) - random date + 1, calculated by days.

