8.1.6. Safety analysis

Safety analysis mainly adopts safety set. All adverse events are coded by MedDRA 20.0 to describe the total number and incidence of adverse events (including serious adverse events), and the

frequency table is used to describe the frequency, severity of each adverse event and its relationship with the treatment. Adverse events relevant (related, probably related, and possibly related) to this research treatment are described and listed separately. Other safety indicators will also be described and summarized. The laboratory changes with clinical significance will be counted as AE.

9. Statistical analysis results

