9.5. Safety analysis (SS)

9.5.1. Adverse event (AE)

Table 62. Between-group comparison of AE

Items	Experimental group			Control group			P-value
	No. of AEs	No. of subjects	Percentage	No. of AEs	No. of subjects	Percentage	
AE							
AE of severe severity							
Drug-related AE							
Serious adverse event (SAE)							
Drug-related SAE							
Drop-out due to AE							
Drop-out due to SAE							

Note 1: The definitions related to drugs are “definitely related”, “probably related”, “possibly related”, “unlikely related” and “not related”.

Note 2: The data of SAE that cause the drop-out came from the external file “XX”.

Table 63. characteristics of AE in each group

Items	Experimental group			Control group			P-value
	No. of AEs	No. of subjects	Incidence	No. of AEs	No. of subjects	Incidence	
Relationship with study drug							
Definitely related							
Probably related							

Items	Experimental group			Control group			P-value
	No. of AEs	No. of subjects	Incidence	No. of AEs	No. of subjects	Incidence	
Possibly related							
Unlikely related							
Not related							
Outcome	Recovered/resolved						
	Recovered/resolved with sequelae						
	Not recovered						
	Recovering/resolving						
	Death						
	Unknown						

Table 64. Between-group comparison of SAE

Items	Experimental group (n=XX)			Control group (n=XX)			Total (n=XX)	P-value
	No. of AEs	No. of subjects	Incidence (%)	No. of AEs	No. of subjects	Incidence (%)		
Results in death								
Requires hospitalization								
Prolongs hospitalization								
Disability								
Dysfunction								
Congenital malformation								
Life threatening								
Other								

Table 65. Summary of AE base on SOC and PT coding

Indicator	Experimental group (n=XX)			Control group (n=XX)			Total (n=XX)	P-value
	No. of AEs	No. of subjects	Incidence (%)	No. of AEs	No. of subjects	Incidence (%)		
AE								

Indicator	Experimental group (n=XX)			Control group (n=XX)			Total (n=XX)			P-value
	No. of AEs	No. of subjects	Incidence (%)	No. of AEs	No. of subjects	Incidence (%)	No. of AEs	No. of subjects	Incidence (%)	
SOC1										
PT1										
PT2										
...										
SOC2										
PT1										
PT2										
...										

Table 66. Summary of adverse reactions base on SOC and PT coding

Indicator	Experimental group (n=XX)			Control group (n=XX)			Total (n=XX)			P-value
	No. of AEs	No. of subjects	Incidence (%)	No. of AEs	No. of subjects	Incidence (%)	No. of AEs	No. of subjects	Incidence (%)	
Adverse event										

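### As written, relapse counts as an adverse event and nothing removes it from the safety tables, so the overall AE and SAE comparisons would mix efficacy with toxicity

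*Protocol*

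**What the plan says.** **Collection.** Protocol 8.3 introduces its list with "The information of AEs to be collected in this research includes the following aspects". The items are "Endpoint event", events the investigator judges related to the test drugs, and serious adverse events. SAP 8.1.3 identifies the first item: a relapse by visit 9, or at an unscheduled visit within 365 days of randomization, is "defined as the occurrence of endpoint events".

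**Definitions.** Protocol 8.1 defines an AE, regardless of causality, as "adverse medical conditions or deterioration of the original medical condition after or during drug treatment". One of the seriousness criteria in Protocol 8.2 is "Requiring hospitalization or extension of the original length of stay". Neither section makes an exception for relapse or for admission because of it. Protocol 8.4 has every SAE recorded, whatever its cause.

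**Analysis.** SAP 8.1.6 codes all adverse events "to describe the total number and incidence of adverse events (including serious adverse events"), and counts clinically significant laboratory changes as AEs. The main display is "Table 62. Between-group comparison of AE", with P-values on its overall AE and SAE rows. Table 64 compares SAEs by seriousness criterion, including hospitalization. Neither SAP 8.1.6 nor the notes in SAP 9.5.1 exclude endpoint events.

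**The concern.** The trial's objective is to find the more effective and the safer of two drugs, which calls for two separate answers. If a relapse counts as an AE, a drug that prevents relapses has fewer AEs for that reason alone. The overall rows would then tend to favour the more effective drug whatever its toxicity. A real excess of toxicity on that drug could be offset by its fewer relapses. Conversely, equal toxicity could be reported as a safety advantage. These overall rows are the ones most readily quoted as the safety result.

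**Working it through.** **Inputs from the documents.** One-year relapse-free survival is 0.56 (MMF) and 0.70 (tacrolimus), with 135 children per arm (Protocol 3.3.2); tests are two-sided at 0.05 (Protocol 11.2.1). As a check that these are the planning rates, ln(0.70)/ln(0.56) = 0.6151, the hazard ratio in Protocol Appendix 4. The planned one-year relapse proportions are therefore 0.44 and 0.30, or about 59 and 41 children (135 × 0.44 = 59.4; 135 × 0.30 = 40.5).

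**Inputs not in the documents.** The incidence of non-relapse AEs, their overlap with relapse, and the share of relapsing children admitted are assumptions, shown over ranges.

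**1. Any-AE incidence with equal toxicity.** Let p be the non-relapse AE incidence in both arms and q the share of relapsing children who have no other AE, also equal in both arms. Any-AE incidence is p + 0.44q (MMF) and p + 0.30q (tacrolimus), so the gap is 0.14q. If relapse and other AEs are independent, q = 1 − p and the gap is 0.14 × (1 − p):

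| p | MMF | Tacrolimus | Gap (points) |
|---|---|---|---|
| 0.2 | 55.2% | 44.0% | 11.2 |
| 0.3 | 60.8% | 51.0% | 9.8 |
| 0.5 | 72.0% | 65.0% | 7.0 |
| 0.8 | 88.8% | 86.0% | 2.8 |

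If every relapsing child already has another AE, q = 0 and the gap is zero. At p = 0.3 under independence, a pooled-variance normal approximation with 135 per arm gives about a 37% chance of a significant result favouring tacrolimus although toxicity is equal.

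**2. How large an excess could be cancelled.** Under independence the totals match when (1 − pT) × 0.70 = (1 − pM) × 0.56, that is pT = 0.20 + 0.80 × pM, where pT and pM are the non-relapse AE incidences on tacrolimus and MMF.

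| True MMF | True tacrolimus | Total shown in both arms | Power, relapse excluded |
|---|---|---|---|
| 20% | 36% | 55.2% | 84% |
| 50% | 60% | 72.0% | 38% |
| 80% | 84% | 88.8% | 13% |

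In each row, including relapse leaves only a 2.5% chance of a significant result in the tacrolimus-excess direction. The loss is substantial only in the first row; the other two excesses would usually be missed anyway.

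**3. SAEs.** Let h be the share of relapsing children admitted. Admission for relapse alone contributes 0.44h (MMF) and 0.30h (tacrolimus). With non-relapse SAEs at 5% in both arms and independence, the gap is 0.95 × 0.14 × h. The last column takes a true non-relapse SAE rate of 5% on MMF and 15% on tacrolimus, for which power is 78.5% with relapse excluded.

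| h | Relapse SAEs, MMF vs tacrolimus | Gap at equal 5% (points) | Power for 5% vs 15%, relapse included |
|---|---|---|---|
| 5% | 2.2% vs 1.5% | 0.7 | 65% |
| 10% | 4.4% vs 3.0% | 1.3 | 52% |
| 25% | 11.0% vs 7.5% | 3.3 | 24% |
| 50% | 22.0% vs 15.0% | 6.7 | 5% |

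**The case against.** The best counter-argument is that the documents handle relapse apart from safety. The flow chart has one row for relapse and another for adverse events. Protocol 8.3 itself later names a potential endpoint alongside AEs and SAEs, as if it were a different category. Endpoint events are adjudicated for the effectiveness analyses (SAP 8.1.2). Relapses are listed in Tables 117–120 and AEs and SAEs in Tables 128–131. The note to Table 1 counts withdrawal for the endpoint event as completing the trial. On this view the items in 8.3 are three capture streams, and relapse was never meant for Table 62. This shows that intent is uncertain, and it rules out saying that relapse will certainly be counted. It supplies no exclusion rule, however, and the wording of 8.1 and 8.3 points towards inclusion.

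A reader might infer that the whole safety assessment is compromised. The documents do not support that. Table 62 has separate drug-related rows, Table 65 would show relapse under its own coded term, and Table 66 is confined to adverse reactions. Renal, hepatic, glucose and blood-count results have their own tables. Drug-related rows depend on attribution in an open-label trial, but they are less exposed than the totals.

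A reader might also note that the tacrolimus reaction list in Protocol 8.1.1 includes "Membranous glomerulonephritis, hydronephrosis, nephromegaly, and nephrotic syndrome", while the MMF list does not mention nephrotic syndrome, and infer that relapse will be classified differently by arm. The SAP attaches no analysis to those lists and codes AEs in both arms with MedDRA. If attribution did differ, it would add reactions to tacrolimus rather than hide them.

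Independence is also open to challenge. Protocol 5.2.2 anticipates relapse accompanied by infection, so some relapsing children would already have an AE. It describes steroid adjustment without mentioning admission, so the high admission shares above have no support in the documents.

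**Conclusion.** The point holds in limited form. On the text as it stands, relapse is an AE, and an SAE when it leads to admission, and no rule removes it from the analysis. The exposed results are mainly the overall AE and SAE rows of Table 62 and the hospitalization row of Table 64.

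At the planned relapse rates, efficacy alone would separate the arms by 0.14 × (1 − p) in any-AE incidence, 7.0 points at p = 0.5. This assumes equal non-relapse AE incidence, independent of relapse, and is smaller where the same children have both. The direction rests on the plan's expectation of fewer relapses on tacrolimus: the gap vanishes if relapse rates are equal and reverses if tacrolimus has more. It would therefore be wrong to conclude that the tables must hide tacrolimus toxicity. The SAE effect cannot be sized from the documents; under the assumptions above it is modest at admission shares of 5–10%.

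**What to change.** In SAP 8.1.6 and Tables 62 and 64:

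- Make the main overall AE and SAE rows, and the hospitalization row, exclude protocol-defined relapse and admission solely for relapse.
- Show relapse and admission for relapse as separate rows, with relapse-included totals as a supplement.
- Identify relapses from the dates already listed in Table 117, and code them the same way in both arms.
- Leave SAE reporting under Protocol 8.4 unchanged.

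The exclusion must use the same relapse definition as the primary endpoint. Protocol 7.2.4 and SAP 6.2.4 print different dipstick grades, and the two must be reconciled first.

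No new data field is required. SAP 4.1 describes enrollment as completed, so an added eCRF flag could come too late. The cost is SAP wording, a few table rows, and a judgement on which admissions were solely for relapse. That judgement should follow a written rule applied without knowledge of treatment arm.
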